3.3.3. Criteria for Early Discontinuation of a Cohort (Stopping Rules)

3.3.3.1. Stopping Rules for Cohorts 1 to 4 and 8 (Phase 1a)

Dosing of an individual cohort (ie, 1, 2, 3, 4 or 8) will be suspended when:

- 2 or more participants in each cohort (Cohort 1, 2, or 3) or cohorts with the same high-dose level (Cohorts 4 and 8) experience a treatment-emergent, investigational product-related Grade 3 or higher clinical AE with the same preferred term (with the exception of headache, nausea, measured grades of erythema, or edema/induration)
- 1 or more participants in each cohort (Cohort 1, 2, or 3) or cohorts with the same high-dose level (Cohorts 4 and 8) experience a treatment-emergent, investigational product-related SAE
- 2 or more participants in each cohort (Cohort 1, 2, or 3) or cohorts with the same high-dose level (Cohorts 4 and 8) experience confirmed treatment-emergent, investigational product-related Grade 3 or higher clinically significant laboratory abnormality (as determined by the investigator based on clinical evaluation of the participant) unless there is an obvious physiological explanation for the event
- The number and/or severity of AEs justifies discontinuation of the study

Decisions to reinitiate a study cohort will be made by the sponsor in consultation with the investigators and pending a safety review by the SRT of all safety data generated in participants dosed to date. For individuals already receiving investigational product, the decision whether to complete the full course of study treatment will be made by the sponsor with disclosure of new information to the study participant.

3.3.3.2. Stopping Rules for Cohorts 5 to 7 (Phase 1b)

Dosing of an individual cohort (ie, 5, 6, or 7) will be suspended when:

- 2 or more participants in Cohort 5 or cohorts with the same high-dose level (Cohorts 6 and 7) experience a treatment-emergent, investigational product-related Grade 3 or higher clinical AE with the same preferred term (with the exception of headache, nausea, measured grades of erythema, or edema/induration).
- 2 or more participants in Cohort 5 or cohorts with the same high-dose level (Cohorts 6 and 7) experience confirmed treatment-emergent, investigational product-related Grade 3 or higher clinically significant laboratory abnormality (with the exception of clinically insignificant Grade 3 or 4 cholesterol, triglyceride, or glucose). Alanine aminotransferase (ALT) elevations without any evidence of hepatic injury are excluded and will be managed and followed up based on the guideline provided in Section [7.7.4](#) and [Table 11](#).
- The number and/or severity of AEs justifies discontinuation of any study cohort.

An SRT review of all safety data generated in participants who have received investigational product will be initiated. No new participants will be enrolled or initiated on investigational product; however, for individuals already receiving the investigational product, the decision whether to complete the full course of investigational product will be made by the sponsor, investigator, and where applicable or required, by review by regulatory agencies with disclosure of new information to the study participants.

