Initiation of Cohort 8 will be determined at the discretion of the SRT based on the evaluation of available safety data through Day 43 (14 days after all participants in Cohort 3 have completed the initial dose of both investigational products), in addition to all available safety data from prior cohorts. Initiation of a third dose of 2-vector combination therapy will be determined at the discretion of the SRT based on the evaluation of the available safety data through Day 99 (14 days after all participants in Cohort 4 have completed the second dose of both investigational products), in addition to all available safety data. The decision on cohort initiation will be based on prespecified criteria agreed upon by the SRT and documented in the SRT charter. The duration of this review period may be increased based on the emerging and cumulative safety data.

Cohort 6

Initiation of Cohort 6 will be determined at the discretion of the SRT based on the evaluation of available safety data through Day 43 (14 days after initial dose of both the investigational products for all participants enrolled in Cohort 4), available safety data from participants enrolled

in Cohort 5, and all available safety data from all dosed cohorts, and dosing will be initiated only in the absence of dose-limiting toxicity and/or meeting any prespecified stopping criteria. The duration of this review period may be increased based on the emerging and cumulative safety data.

Cohort 7

Initiation of Cohort 7 will be determined at the discretion of the SRT based on the evaluation of available safety data through Day 43 (14 days after initial dose of both the investigational products for all participants enrolled in Cohort 4), available safety data from participants enrolled in Cohort 5, and all available safety data from all dosed cohorts. Initiation of the third dose of 2-vector combination therapy will be determined at the discretion of SRT based on the evaluation of the available safety data through Day 99 (14 days after all participants in Cohort 4 have completed the second dose of both investigational products), in addition to all available safety data. The decision on cohort initiation will be based on prespecified criteria agreed upon by the SRT and documented in the SRT charter. The duration of this review period may be increased based on the emerging and cumulative safety data.

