3.1.1. Safety Review Team and Charter

An SRT will make decisions on initiating enrollment of higher dose cohorts and initiating the third dose of both investigational products based on available safety data in prior study cohorts as described in Section 3.1. There will be 3 planned SRT reviews in this protocol. Ad hoc reviews can be convened at the discretion of the SRT during the study based on new safety concerns and/or the protocol stopping rules (Section 3.3.3).

An SRT charter defining the team membership, meeting conduct, and decision-making process will be agreed upon by all team members before the first meeting. The data reviewed at the team meetings to make cohort transition decisions will be defined in the charter. The quality control checks performed on the data reviewed and used for making these decisions will also be described in the charter.

Source data verification may not be performed before SRT meetings. Alternative data quality control checks that are performed on data used to make dosing continuation or transition decisions are described in the SRT charter.

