7.4.1.1. Electronic Serious Adverse Event Reporting Process

Site personnel will record all SAE data on the applicable eCRFs and from there transmit the SAE information to PS within 24 hours of the investigator’s knowledge of the event from ICF signature throughout the duration of the study, including the protocol-required posttreatment follow-up period.

If it is not possible to record and transmit the SAE information electronically, record the SAE on the paper SAE reporting form and transmit the report within 24 hours:

Patient Safety

Email: [contact]
or
[contact]

If an SAE has been reported via a paper form because the eCRF database has been locked, no further action is necessary. If the database is not locked, any SAE reported via paper must be transcribed as soon as possible on the applicable eCRFs and transmitted to PS.

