2.1.1. Dose Escalation Analysis

For the purposes of making the decision to escalate from the low dose to the high dose or to increase the number of (high-dose) alternating viral vector courses of treatment from 2 to 3 courses, interim analyses of relevant safety data will be conducted by Gilead. These dosing decisions will be determined at the discretion of the SRT based on stopping rules and the criteria outlined in the protocol and SRT Charter. Safety assessments (eg, AEs, ECGs, laboratory test results) will be displayed by population and cohort to facilitate the decision to dose escalate while preserving the blind at the participant level. Three planned SRT meetings will occur when a minimum of the following data is available:

Safety data through 14 days (Day 43) after the initial dose of both investigational products for all participants enrolled in Cohort 3 in addition to all available safety data from Cohorts 1 and 2.

Purpose: Initiation of Cohorts 4, 5 (to be run concurrently) and Cohort 8.

Available safety data through 14 days (Day 43) after initial dose of both investigational products for all participants enrolled in Cohort 4 in addition to all available safety data at the time of the snapshot. Purpose: Initiation of Cohort 6 and Cohort 7 (see paragraph below for additional criteria required for Cohorts 7 and 8 and dosing of 3rd course of alternating viral vector therapy).

Safety data through 14 days (Day 99) after all participants in Cohort 4 have completed the second dose of both investigational products (total 4 doses) in addition to all available safety data. Purpose: Initiation of a third dose of 2-vector alternating combination therapy in Cohorts 7 and 8.

The SRT may lengthen the duration of follow-up required for planned SRT meetings and/or hold additional ad-hoc SRT meetings at their discretion.

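### The CHB cohorts have no suspension rule for a single related SAE, although healthy cohorts on the same doses and schedules do

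*Protocol*

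**What the plan says.** Protocol 3.3.3.1 (Cohorts 1 to 4 and 8) lists four grounds for suspending dosing. One is met when a single participant in Cohort 1, 2 or 3, or in Cohorts 4 and 8 taken together, is found to "experience a treatment-emergent, investigational product-related SAE".

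Protocol 3.3.3.2 (Cohorts 5 to 7) opens with "Dosing of an individual cohort (ie, 5, 6, or 7) will be suspended when" and lists three grounds. The first two are numeric and need at least two participants: related Grade 3+ clinical events with the same preferred term, and confirmed related Grade 3+ clinically significant laboratory abnormalities. The third is a judgement: "The number and/or severity of AEs justifies discontinuation of any study cohort". There is no SAE ground. When a rule is met, the SRT reviews all safety data and "No new participants will be enrolled or initiated on investigational product". Continuation for those already on product is decided separately.

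Outside these rules, Protocol 3.1.1 says "Ad hoc reviews can be convened at the discretion of the SRT during the study". Protocol 3.1 lets Cohort 6 start on the condition that "dosing will be initiated only in the absence of dose-limiting toxicity and/or meeting any prespecified stopping criteria". SAP 2.1.1 says that dosing decisions are taken by the SRT "based on stopping rules and the criteria outlined in the protocol and SRT Charter"; it adds no rule of its own.

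**The concern.** This is a first-in-human product with safety as the primary objective. Phase 1b participants get the same dose levels and schedules as their healthy counterparts but lack one of the protections those counterparts have. A single related SAE in a CHB participant, however severe, meets no numeric trigger. Several related SAEs with different preferred terms meet no numeric clinical trigger either. Whether enrolment and new starts pause, and whether the SRT meets, then depends on someone invoking the judgement clause or calling an ad hoc review.

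The CHB population is not an obvious place to relax the rule. Protocol 1.1 describes therapeutic vaccines as driving HBV-specific responses against infected hepatocytes, and the healthy cohorts must be HBV-negative (Protocol 4.2.1), so Phase 1a cannot reveal that hazard. Phase 1b also runs at about 15 sites rather than one (Protocol 3.1), with at least 2 hours of post-dose observation rather than 4 (Protocol 5.3).

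The gap extends to escalation. A related SAE in Cohort 5 would not by itself meet a numeric stopping criterion for the Cohort 6 start condition, and the protocol does not define dose-limiting toxicity.

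**Working it through.** **Comparison of the rules**

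| Ground for suspension | 3.3.3.1 (healthy) | 3.3.3.2 (CHB) |
|---|---|---|
| Related Grade 3+ clinical AE, same preferred term | 2 or more participants | 2 or more participants |
| Confirmed related Grade 3+ laboratory abnormality | 2 or more participants | 2 or more; ALT elevations without hepatic injury excluded |
| Number and/or severity of AEs | judgement | judgement |
| Related SAE | 1 or more participants | none |

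Protocol Table 8 gives the dose and schedule match: Cohort 5 with 3 (low dose, Days 1, 29, 57, 85), Cohort 6 with 4 (high dose, same days), Cohort 7 with 8 (high dose, plus Days 113 and 141). The ALT exclusion refers the reader to 7.7.4 and Table 11. Nothing accounts for the missing SAE ground: the Amendment 1 entry says only that stopping rules were aligned with European Medicines Agency requirements, and the Amendment 2 entry only that same-dose cohorts are pooled.

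**How often the gap might matter**

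The plan states no operating characteristics for these rules, so there is no figure to reproduce. It also gives no related-SAE rate. I assume *s* = 2% to 5% per participant, independent between participants. Protocol 8.8 gives 8 active and 2 placebo per cohort: 8 active (10 in all) in Cohort 5, and 16 active (20 in all) in Cohorts 6 and 7, which the rule pools. These are probabilities of events, not of suspension.

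*Exactly one participant with a related SAE*, n·s·(1−s)^(n−1):

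- n = 8: 8 × 0.02 × 0.98^7 = 0.139; 8 × 0.05 × 0.95^7 = 0.279
- n = 16: 16 × 0.02 × 0.98^15 = 0.236; 16 × 0.05 × 0.95^15 = 0.371
- Counting placebo participants at the same rate: n = 10, 0.167 to 0.315; n = 20, 0.272 to 0.377

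*At least one*, 1 − (1−s)^n: n = 8, 0.149 to 0.337; n = 16, 0.276 to 0.560. If all related SAEs had different preferred terms, this would be the chance of one or more with no numeric clinical trigger met.

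*Onset before the participant's own last dose*, assuming onset uniform over follow-up. The last dose falls 84 of 252 days in for Cohorts 5 and 6 (Day 85 of 253) and 140 of 308 days in for Cohort 7 (Day 141 of 309), so *s* is multiplied by 0.333 or 0.455. Chance of exactly one:

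- 8 active: 0.051 to 0.119
- 16 active (8 + 8): 0.112 to 0.234
- All 10: 0.063 to 0.143
- All 20 (10 + 10): 0.136 to 0.270

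*Allowing the existing clinical trigger to fire anyway.* Suppose non-serious related Grade 3+ events sharing the SAE's term also occur in *g* = 5% to 10% of participants, and the SAE is itself Grade 3+. The chance of exactly one SAE with no clinical trigger met is n·s·(1−s−g)^(n−1):

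| | g = 5% | g = 10% |
|---|---|---|
| n = 8, s = 2% | 0.096 | 0.065 |
| n = 8, s = 5% | 0.191 | 0.128 |
| n = 16, s = 2% | 0.108 | 0.047 |
| n = 16, s = 5% | 0.165 | 0.070 |

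The laboratory trigger and the judgement clause are not modelled.

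**The case against.** The best case for the plan is that the two sections were drafted for different situations. Section 3.3.3.2 has its own laboratory exceptions, and the rules were touched in both amendments, so the omission may be deliberate. CHB participants meet each dose level only after healthy participants have: Cohort 5 after Cohort 3 Day 43 data, Cohorts 6 and 7 after Cohort 4 Day 43, third doses after Cohort 4 Day 99. The judgement clause can be met by one severe event, so a cohort-level mechanism exists.

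Those judging are also well informed. The medical monitor is unblinded (Protocol 5.1.2), sites must "transmit the SAE information to PS within 24 hours", SUSARs go to regulators and ethics committees (7.5), and either body can have the study stopped (3.3.4). Anaphylaxis and new immune-mediated conditions end dosing for the individual (1.5). The SRT charter, which is not available, may contain an SAE criterion.

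All of this is true, and it narrows the gap to automatic versus discretionary suspension. It does not close it. The reporting, monitoring and individual-level safeguards apply equally in Phase 1a, where the SAE rule was still thought necessary. The Day 43 gates cover only the first dose of each vector, and Cohort 5 runs alongside Cohort 4. HBV-negative volunteers cannot show toxicity directed at infected liver cells.

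The objection to the probabilities also has force. The rates are assumed. Whole-study figures include 24 weeks after the last dose, and even the dosing-window figures include time when enrolment may be complete and a pause on new starts has no effect. If the SAE's term differs from that of the non-serious events, the last set of figures rises from 7% to 19% up to 12% to 27% (n = 8), and from 5% to 16% up to 13% to 30% (n = 16). The range depends on the assumptions; the textual finding does not.

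**Conclusion.** The concern holds. As written, one related SAE in Cohorts 5 to 7 triggers no rule-based suspension, whereas in the matching healthy cohorts it does, and neither document gives a reason. The difference rests on the text alone and is certain.

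How often it would matter is only illustrated. At an assumed related-SAE rate of 2% to 5%, a lone affected participant among the active participants is far from remote, and remains plausible when only the dosing period is counted. What the SRT would do in that event cannot be determined without its charter. This is an inexpensive patient-safety improvement that should be made; it does not invalidate the design.

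**What to change.** Add a fourth bullet to Protocol 3.3.3.2, mirroring 3.3.3.1: suspend dosing when one or more participants in Cohort 5, or in Cohorts 6 and 7 combined, have a treatment-emergent SAE judged related to investigational product. If wanted, keep ALT elevations without evidence of hepatic injury outside this trigger and under 7.7.4 and Table 11, as the laboratory bullet already does. That avoids pausing a cohort for an event where Table 11 may allow product to continue.

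The cost is one protocol bullet whose wording already exists, plus possible extra temporary pauses for SRT review. Participants already on product would still be handled case by case under the existing text. If the omission is deliberate, 3.3.3.2 should give the reason, though that alone would leave the protection unchanged.

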3.3.4. Criteria for Early Termination of the Study

The study will be stopped in the following instances:

- On recommendation of the SRT based on review of the available safety data
- Discontinuation of the study at the request of Gilead Sciences (Gilead) or a regulatory agency or an independent ethics committee (IEC)

3.3.5. Reporting a Loss to Follow-Up

Should the participant fail to return to the study site for a scheduled protocol-specified visit, the site will need to make at least 3 attempts by a combination of telephone, email, or mail to contact the participant. The site must document all attempts to contact the participant. If a participant does not respond within 3 months after the initial contact, the participant will be considered lost to follow-up and no additional contact will be required.

3.4. Definitions for Time of Primary Endpoint and End of Study

3.4.1. Primary Endpoint

The date for the last participant last visit for the primary endpoint is the date of the last visit to perform assessments for the final analysis.

3.4.2. End of Study

The end of the study is defined as the last participant's last observation (or visit).

3.5. Source Data

The source data for this study will be obtained from the participating sites, central laboratory, specialty laboratory, the Interactive Response Technology (IRT), and/or other vendors as designated by the sponsor.

4. PARTICIPANT POPULATION

4.1. Number of Participants and Participant Selection

Approximately 80 unique participants will be enrolled in the study; study participants will include male and nonpregnant, nonlactating, female participants aged 18 through 60 years in Phase 1a cohorts, and aged 18 through 65 years in Phase 1b cohorts. As described in Section 3.1, participants who will be enrolled in:

- Phase 1a cohorts will be healthy participants
- Phase 1b cohorts will have confirmed CHB and will be virally suppressed

Enrollment of participants of both sexes is encouraged. Participants will be enrolled from several sites across the countries where the study will be conducted. Within these countries, recruitment efforts will be broad enough to capture a fair representation of the population but, due to the small sample size per study cohort, no specific quotas will be provided by race and/or ethnicity.

4.1.1. Participant Replacement

If necessary, replacement participants may be enrolled after discussion and approval from Gilead if a current participant is considered nonevaluable. Replacement participants will not be enrolled for participants who discontinue the study due to investigational product-related AEs. Sites will be encouraged to make efforts to retain all individuals who may wish to discontinue the study due to AEs. Ideally, such participants will receive no further investigational product but will continue all visits on schedule.

The primary outcome of interest in this study is the safety and tolerability of GS-2829 and GS-6779 used in combination, so participants who receive only 1 of the 2 vectors and discontinue the study for non-AE related reasons and participants requiring prolonged systemic steroid therapy may be replaced to ensure the collection of evaluable data but will be encouraged to remain on study for evaluation of safety.

4.2. Phase 1a Healthy Participant Inclusion/Exclusion Criteria

4.2.1. Inclusion Criteria

Phase 1a participants must meet all of the following inclusion criteria at screening (or as stated otherwise) to be eligible for participation in this study:

- 1) Have the ability to understand and sign a written informed consent form (ICF), which must be obtained prior to initiation of study procedures.
- 2) Assigned male sex at birth or female sex at birth (and be nonpregnant and nonlactating).

- 3) Participants assigned male at birth and participants assigned female at birth and of childbearing potential who engage in heterosexual intercourse must agree to use protocol-specified methods of contraception as described in Appendix 11.4.
- 4) Be aged 18 through 60 years, inclusive, at enrollment.
- 5) Have a calculated body mass index (BMI) of $\leq 32.0 \text{ kg/m}^2$.
- 6) Must, in the opinion of the investigator, be in good health based upon medical history and physical examination, including vital signs.
- 7) Laboratory evaluations and 12-lead electrocardiogram (ECG) evaluations must be without clinically significant abnormalities as assessed by the investigator.
- 8) Nondiabetic with a hemoglobin A1c $< 6.5\%$.
- 9) Must be willing and able to comply with all study requirements.
- 10) No prior history of HBV infection with a negative HBsAg and hepatitis B core antibody.
- 11) Have liver biometric tests such as ALT, aspartate aminotransferase (AST), alkaline phosphatase (ALP), and total bilirubin at or below the upper limit of normal (ULN).
- 12) Have a calculated creatinine clearance (CL_{cr}) of at least 90 mL/min (using the Cockcroft-Gault method {[Cockcroft 1976](#)}) based on serum creatinine and actual body weight as measured for:
 - Participant assigned **male** at birth:
$$\frac{(140 - \text{Age [years]}) \times (\text{Weight [kg]})}{72 \times (\text{Serum Creatinine [mg/dL]})} = \text{CL}_{\text{cr}} \text{ (mL/min)}$$
 - Participant assigned **female** at birth:
$$\frac{(140 - \text{Age [years]}) \times (\text{Weight [kg]}) \times 0.85}{72 \times (\text{Serum Creatinine [mg/dL]})} = \text{CL}_{\text{cr}} \text{ (mL/min)}$$

